18. CONCURRENT EMBEDDED QUALITATIVE STUDY

The aims of this qualitative study are to explore:

- Patient, informal caregiver and HCP, experience and acceptability of LVP and LTADs and factors that account for variability in experience and acceptability.
- "Real life" implementation of LTAD factors which may impact on embedding the intervention in standard practice.
- Relationship between trial outcomes (especially HRQoL and symptoms) and perceptions

We will undertake a series of semi structured interviews with patients (n=30, 15 per group), informal caregivers (n=20, 10 per group) and HCP (n=20). Sample sizes are informed by the principles of information power and saturation. (84) Patients with a range of demographics, socioeconomic status, and geographic location will be sampled to ensure diverse experiences are captured. Life expectancy in refractory ascites is limited, and we recognise that patient/caregiver beliefs and experiences may change across the period. We will therefore aim to recruit patients/informal caregivers who have been in the study for different durations but ensure that they have had at least one round of intervention, be that drainage in hospital or at home. A patient can still take part if their caregiver declines and vice versa. Similarly, we aim to capture a range of HCP views from those individuals involved in delivering the intervention (e.g. gastroenterologists, hepatologists, hospital and community nurses), at a range of different study sites. We hope this will give us a broad scope on intervention practices and views from teaching and district general hospitals. Interviews will start during the pilot phase and we will aim to recruit proportionate to overall recruitment i.e. we aim to complete 15% of participant interviews in the pilot, with the remaining 85% completed in the main trial. These interviews

will help us ensure we capture a representative sample and will allow us to address any recruitment issues.

Topic guides for the interviews will be collaboratively developed with the PPI and clinical members of the research team. Interview themes will include an exploration of: experiences of recruitment, participation, LTAD/LVP and end of life care; beliefs about the role and value of LTAD in refractory ascites, practical steps and barriers involved in undertaking LTAD, and caregiver/HCP perspectives. Topic guides for patients and informal caregivers will mirror each other, using broad prompts to ask about HRQoL and the experience of LTAD/LVP (in line with the primary study objective), decision making at joining the study (aimed at the secondary objective of perceptions). Patients will be asked how their experiences could be improved while informal caregivers will be asked about any additional support they need. Participants will be given the opportunity to add in anything they feel is important to say. HCP will have a separate topic guide, focusing on the decision-making process for LTAD/LVP, perceived impact of the intervention, practical implications and implementation. Again, HCPs will be able to add any further comments or topics that they felt was missing during the interview. These topic guides are deliberately intended to be followed loosely, allowing researchers to follow the thread of conversation as led by the participant. Completed interviews will be reviewed across the study to amend the topic guide as necessary, incorporating any elements which seem to reoccur.

The interviews will be conducted by experienced SHORE-C researchers by phone or video link. It is estimated interviews will take between 15-45 minutes, dependent on how much or how little a participant wants to say. To reduce participant burden, breaks will be allowed during the interviews and participants will be reminded that they can stop the interview at any time without giving a reason. Interviews will be digitally recorded, transcribed and analysed.

The research team member will provide patients and informal caregivers with information about the optional interview within their main information sheets. HCP will receive an information sheet solely about the interviews. All participating individuals have a unique consent for the interviews, separate to the main study. These will be audio-recorded but a paper copy will be provided so as to inform participants what they will be asked ahead of the interview. The qualitative researcher will contact participants, and after addressing any questions or concerns arrange a convenient time for the interview. The audio-recorded consents will be stored as an encrypted file, separate to the interview itself. Encrypted audio files of the interview will only be stored for as long as it takes to transcribe the interview and will be deleted after the transcripts are checked for accuracy.

19. PARTICIPANT WITHDRAWAL

Participants will be able to withdraw from the study at any time until the study has closed, without it affecting their future routine care. The reasons for withdrawal include, but are not limited to, the following:

- Patient death
- A request by a participant to withdraw from the study
- Serious adverse reaction
- Significant deviation from the study protocol, assessed on a case-by-case basis after discussion with the CI and TMG.

20. STORAGE AND ANALYSIS OF CLINICAL SAMPLES

Routine clinical bloods will be analysed on the day of collection. In addition, an optional 20 ml of blood will be collected (10 ml saved as serum, and 10ml as whole blood). Throughout the study, the research blood samples will be stored at sites, and subsequently sent at the end of the study to the Clinical Investigations and Research Unit (University Hospitals Sussex) for analysis into advanced cirrhosis to include but not limited to bacterial DNA levels, lipopolysaccharide binding protein, tumour necrosis factor and interleukin 6. It may also include genetic testing if during the course of the study, new genetic biomarkers are identified. All research blood samples will be destroyed in accordance with the hospital procedures at the end of the study.

A lab manual will be provided to sites for the handling and storage of the research blood samples.

21. DEFINITION OF THE END OF STUDY

The study will end after the final follow-up data is collected after the 3-month Follow-Up visit, or death, or withdrawal of the last recruited participant.

22. SAFETY REPORTING

Term	Definition		
Adverse Event (AE)	Any untoward medical occurrence in a participant to whom an intervention has been administered, including occurrences which are not necessarily caused by or related to that intervention.		
Adverse Reaction (AR)	An untoward and unintended response in a participant to the intervention		
Serious Adverse Event (SAE)	 A serious adverse event is any untoward medical occurrence that: results in death is life-threatening requires inpatient hospitalisation or prolongation of existing hospitalisation results in persistent or significant disability/incapacity 		

 Table 4 Definitions of Safety Reporting Terms

	consists of a congenital anomaly or birth defect
	Other 'important medical events' may also be considered serious if they jeopardise the participant or require an intervention to prevent one of the above consequences.
	NOTE: The term "life-threatening" in the definition of "serious" refers to an event in which the participant was at risk of death at the time of the event; it does not refer to an event which hypothetically might have caused death if it were more severe.
Serious Adverse Reaction (SAR)	An adverse event that is both serious and, in the opinion of the reporting Investigator, believed with reasonable probability to be due to one of the Study treatments, based on the information provided.

22.1. Assessing Relatedness of AE/SAEs

AE/SAEs will primarily be assessed for relatedness to the study interventions at the site by the Principal Investigator, or an investigator delegated to do so. Unrelated events will include but are not limited to the following:

- Hepatic encephalopathy
- Gastrointestinal bleeding related to peptic ulceration, hypertensive portal gastropathy or varices
- Liver cancer and or its treatment
- Complications of gastroscopy (perforation, bleeding)
- Complications of drug treatment for cirrhosis (lactulose, beta blockers, terlipressin, antibiotics, diuretics)
- Death related to the liver disease- will include death from liver failure, multiorgan failure, hepatorenal syndrome, variceal bleeding and sepsis

Unrelated events will be recorded in the eCRF but not reported to BSCTU, Sponsor or the REC.

If an event is considered to be related to the study interventions then they will be classified as an Adverse Reaction (AR) or a Serious Adverse Reaction (SAR) and will be assessed for Expectedness, as below.

Any potential SARs are to be recorded on the eCRF *and* reported to the BSCTU via email to [contact] immediately when sites become aware of the event, and at least within 24 hours.

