22.2. Assessing Expectedness of AR/SARs

This study involves a cohort with advanced cirrhosis with a high morbidity and mortality. Hence in this patient population worsening of existing conditions, hospitalisations and acute illnesses are to be expected.

Expected SAR will include the following (only if they result in hospitalisation):

- LTAD or LVP leakage or blockage
- Cellulitis
- Pain at site of insertion not controlled by analgesia
- Bacterial peritonitis
- Sepsis which in the opinion of the PI is directly related to LTAD or LVP
- Death (only if in the opinion of the researchers directly related to the LTAD or LVP)
- Doubling in serum creatinine from baseline
- Bleeding if directly related to LTAD or LVP
- Bowel perforation if directly related to LTAD and LVP
- Failed drainage and or drain displacement

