22.3. Suspected Unexpected SAR (SUSAR)

Any events that in the opinion of the PI are directly related to the intervention and are not listed as expected are considered Suspected Unexpected Serious Adverse Reactions (SUSAR). All SUSARs that occur between participant consent and three months post insertion or death, whichever is earlier, will be recorded on the SAE form and emailed to BSCTU immediately ([contact]), at least within 24 hours of the research team becoming aware in accordance with the BSCTU Safety Reporting SOP. For each SUSAR, relevant information will be collected. All SUSARs will be followed up until resolved or a final outcome reached. The Research Ethics Committee (REC) will be notified of any SUSARs to the study intervention by the BSCTU within 15 days of the chief investigator becoming aware of the event, as per HRA guidance. Any urgent safety measures taken in response to any SUSARs will be reported immediately to the REC and Sponsor.

The CI will have direct and ultimate responsibility for reviewing all reported SARs and SUSARs and will ensure that BSCTU reports these appropriately according to the BSUH SOP on Safety Reporting in Non-CTIMP studies.

Common terminology criteria for adverse events (CTCAE, version 4.03) will be used for assessing AE/SAEs.

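### Sections 22.1 to 22.3 conflict for septic and renal deaths with a drain in place, so a fatal drain infection can miss expedited reporting and central review

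*Protocol*

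**What the plan says.** Section 22.1 starts from an individual judgement: events "will primarily be assessed for relatedness to the study interventions at the site by the Principal Investigator" or a delegate. It then gives examples of unrelated events, one of which is "Death related to the liver disease- will include death from liver failure, multiorgan failure, hepatorenal syndrome, variceal bleeding and sepsis". The consequence of that label is stated next: "Unrelated events will be recorded in the eCRF but not reported to BSCTU, Sponsor or the REC". A potential serious adverse reaction (SAR), by contrast, must go to BSCTU "immediately when sites become aware of the event, and at least within 24 hours".

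Section 22.2 applies to events already judged related. Its list opens with a condition, "Expected SAR will include the following (only if they result in hospitalisation", and includes bacterial peritonitis, a doubling of creatinine, "Sepsis which in the opinion of the PI is directly related to LTAD or LVP" and "Death (only if in the opinion of the researchers directly related to the LTAD or LVP".

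Section 22.3 says that related events which "are not listed as expected are considered Suspected Unexpected Serious Adverse Reactions (SUSAR". These go to BSCTU within 24 hours and to the REC within 15 days. The chief investigator (CI) reviews the SARs and SUSARs that are reported.

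**The concern.** Whether LTADs add to the infection risk of cirrhosis is the safety worry that section 8.3 names, and peritonitis is the first secondary outcome in section 9.5. The deaths that matter most for that worry are septic deaths and deaths with renal or multiorgan failure after a drain infection. These modes of death appear in section 22.1 as examples of unrelated death, while drain-related sepsis, drain-related death and renal deterioration appear in section 22.2 as reactions. Two sites could follow the text in good faith and send the same death down different routes. The trial is open label (section 15.4), so whoever makes the call knows the arm.

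A second problem is that drain-related death is itself on the expected list. That listing takes it out of the SUSAR definition in some circumstances, and SUSARs are the only reactions that section 22 sends to the REC within 15 days.

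**Working it through.** No arithmetic applies. The check is to follow one event, a fatal infection in a participant with an LTAD, through sections 22.1 to 22.3.

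**Step 1: relatedness (22.1).** The site investigator judges whether the death is related to the intervention. Section 16.1 names worsening liver decompensation and worsening renal function among the signs of suspected peritonitis in an LTAD participant. A fatal drain infection can therefore look like the liver failure, hepatorenal or septic deaths that 22.1 gives as unrelated examples. Section 16.1 also has ascitic fluid analysed in the LTAD arm only on clinical suspicion, so laboratory confirmation may be absent. No precedence rule tells the investigator what to do when a death fits both lists.

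**Step 2: the three routes.**

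| Route | Site's call | Hospitalised? | BSCTU within 24 hours | CI review | REC within 15 days |
|---|---|---|---|---|---|
| A | Liver-disease death, unrelated | Either | No | None stated | No |
| B | Drain-related | Yes | Yes, as an expected SAR | Yes | No |
| C | Drain-related | No, for example death at home | Yes, as a SUSAR | Yes | Yes |

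Route A follows from the unrelated example and the eCRF-only rule in 22.1. The Sponsor receives no report on this route either. Route B follows from the 22.1 rule for potential SARs, which makes no exception for expected ones, together with the expected list in 22.2. Section 22 states no explicit Sponsor route for an expected SAR. Route C follows from reading the hospitalisation condition in 22.2 literally: without hospitalisation the death is not on the expected list, so 22.3 makes it a SUSAR.

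**Step 3: compare the routes.** A and B differ only in a site judgement for which the two lists give conflicting cues. B and C differ only in whether the participant was hospitalised, and no reason is given why that should decide whether the REC hears of a drain-related death.

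**Step 4: antibiotics.** Section 22.1 treats complications of antibiotics, as drug treatment for cirrhosis, as unrelated. Section 16.3 specifies a prophylactic antibiotic for both groups for the study duration. The protocol does not say whether complications of that prophylaxis fall under the 22.1 example.

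**The case against.** The best defence is that the lists sort by attribution. The 22.1 item covers only deaths related to the liver disease, 22.2 holds the drain-related counterparts, and the investigator's judgement comes first. This stands to a point. A reader might infer that every death from sepsis, multiorgan failure or hepatorenal syndrome is pre-labelled unrelated, and the qualifier does not support that. But the wording presents these modes as instances of liver-disease death, and no rule or central check covers the overlap.

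A reader might also infer that the expected label lets a drain-related death bypass BSCTU, or that such a death can never reach the REC. Neither is supported. Every potential SAR goes to BSCTU within 24 hours, and on route C the death is a SUSAR. The CI must also see that BSCTU reports under a safety procedure that is not shown.

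There are further backstops. Unrelated events remain in the BSCTU-provided eCRF (sections 22.1 and 26.2). The monitoring committee meets about every six months and monitors adverse events (section 5.1). Peritonitis is counted by arm whatever the attribution (section 9.5), and attrition from death is summarised by group (section 23.5). All of this stands, and it means that the data are kept. None of it is expedited or is stated to review an unrelated call. The pilot's only infection criterion (section 23.2.1) counts LTADs removed for peritonitis, yet section 16.1 does not make removal automatic and leaves the drain in place at death.

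On the lesser examples, a hepatorenal death and a creatinine doubling that leads to hospitalisation are different events, and the antibiotic is given in both arms rather than being the compared intervention. These points call for clarification and do not carry the argument.

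**Conclusion.** The concern holds in a limited form. For septic and renal deaths with a drain in place, sections 22.1 and 22.2 overlap without a precedence rule. A fatal LTAD infection that the site calls unrelated gets no expedited report to BSCTU, Sponsor or REC and no stated central review. Listing drain-related death as expected has a smaller effect: it removes only the 15-day REC notice, and only when the participant was hospitalised.

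The size cannot be put as a number. The protocol does not give the share of drain infections that are fatal or how often sites would call them unrelated. A reader might multiply the arm size by published peritonitis rates, but that would count infections, not misrouted deaths. Nor do the documents show that the related-event count will in fact be too low; they show that the rules allow it.

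The conclusion assumes a literal reading of the hospitalisation condition, and that the unseen safety procedure and monitoring committee terms of reference do not already close the gap.

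**What to change.** Amend sections 22.1 to 22.3 so that they agree:

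- Either remove death from sepsis, multiorgan failure and hepatorenal syndrome from the default unrelated examples, or state that 22.2 takes precedence over them. In both cases require a documented case-by-case relatedness judgement for each such death, reported to BSCTU.
- Take death as an outcome off the expected list, so that any drain-related death follows 22.3 whether or not the participant was hospitalised.
- State how complications of the protocol-specified prophylactic antibiotic are classified.

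The cost is a protocol amendment to short lists and some additional SAE forms for sites and BSCTU.

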22.2. Assessing Expectedness of AR/SARs

This study involves a cohort with advanced cirrhosis with a high morbidity and mortality. Hence in this patient population worsening of existing conditions, hospitalisations and acute illnesses are to be expected.

Expected SAR will include the following (only if they result in hospitalisation):

- LTAD or LVP leakage or blockage
- Cellulitis
- Pain at site of insertion not controlled by analgesia
- Bacterial peritonitis
- Sepsis which in the opinion of the PI is directly related to LTAD or LVP
- Death (only if in the opinion of the researchers directly related to the LTAD or LVP)
- Doubling in serum creatinine from baseline
- Bleeding if directly related to LTAD or LVP
- Bowel perforation if directly related to LTAD and LVP
- Failed drainage and or drain displacement

22.3. Suspected Unexpected SAR (SUSAR)

Any events that in the opinion of the PI are directly related to the intervention and are not listed as expected are considered Suspected Unexpected Serious Adverse Reactions (SUSAR). All SUSARs that occur between participant consent and three months post insertion or death, whichever is earlier, will be recorded on the SAE form and emailed to BSCTU immediately ([contact]), at least within 24 hours of the research team becoming aware in accordance with the BSCTU Safety Reporting SOP. For each SUSAR, relevant information will be collected. All SUSARs will be followed up until resolved or a final outcome reached. The Research Ethics Committee (REC) will be notified of any SUSARs to the study intervention by the BSCTU within 15 days of the chief investigator becoming aware of the event, as per HRA guidance. Any urgent safety measures taken in response to any SUSARs will be reported immediately to the REC and Sponsor.

The CI will have direct and ultimate responsibility for reviewing all reported SARs and SUSARs and will ensure that BSCTU reports these appropriately according to the BSUH SOP on Safety Reporting in Non-CTIMP studies.

Common terminology criteria for adverse events (CTCAE, version 4.03) will be used for assessing AE/SAEs.

22.4. Potential Complications Of The Intervention

Table 5 below summarises the complications seen in the LVP and LTAD group in the REDUCe feasibility study. (46) Rates of complications were similar in both groups except a higher incidence of self-limiting leakage and cellulitis in the LTAD group (none required hospitalisation.

Complication	Recommended management	Incidence observed in the REDUCe trial		
		LTAD	LVP	
Leakage and cellulitis	Leakage usually self-limiting, if persists may need an extra suture. Continue ascites drainage via LTAD	Leakage/cellulitis 41%	Leakage/cellulitis 11%	
	Cellulitis usually results due to leakage and is again self-limiting. If persist may need a short course of antibiotics. Very rarely LTAD needs to be removed and can be re-sited			
Suspected peritonitis	Do a diagnostic tap for cell count and culture from peritoneum as well as taking sample from LTAD. Treat as per usual peritonitis guidelines. Decision to remove LTAD must be made on a case- by- case basis after discussion with patient/caregiver	6%	11%	
	Routine sampling of ascitic fluid from LTAD and or routine blood tests in asymptomatic patients is not recommended.			
Elevation in serum	Manage as clinically indicated	Serum creatinine (µmol/L) (median, IQR)	Serum creatinine (µmol/L) (median, IQR)	
creatinine		Baseline: 109 (79-141)	Baseline: 113.5 (89-134)	
		Week12: 104.5 (81-115.5)	Week 12: 127 (63-158)	
LTAD blockage	Admit to hospital and discuss need for replacement	0%	NA	
LTAD displacement	Admit to hospital if necessary and discuss need for replacement	6%	NA	
Bleeding	Usually self-limiting	0%	5%	

Table 5. Potential long-term abdominal drain and large volume-related complications observed
in the REDUCe feasibility trial

Unable to manage ascites symptoms despite draining 1-2L three times a week from LTAD	Will need LVP in hospital - drain ascitic fluid via LTAD using adaptor with human albumin solution as per standard LVP protocols	13%	NA
---	--	-----	----

Strategies to reduce complications related to the intervention (LTAD)

- Haemostatic function and ascitic fluid analysis (to exclude infection) to be done within seven +/- 3 days of LTAD insertion
- To reduce leakage/cellulitis ensure that
 - Ascites drained to dryness upon LTAD insertion in hospital using human albumin solution
 - Incisions are of appropriate size (may require a suture if too large)
 - The tunnelled portion of the LTAD is not under undue tension
- LTAD to be inserted by experienced clinicians under ultrasound guidance in hospital
- Ensure good communication between hospital and community teams
- Fortnightly home visits for safety monitoring
- Patients who have LTAD inserted will be provided written information about LTAD management in case there is an out of hours hospital admission

